19. TRIAL TIMELINE

The study will start with an internal pilot RCT of two groups in each of the four sites (East of England, London, Devon, and Sussex) and one remote group; groups will be run in the Autumn 2024 and Spring 2025 academic terms. Should we meet our STOP/REVIEW/GO criteria, the full RCT would then bring on two additional sites (Oxford and Nottingham) and run a further 2 MAC groups in all six sites plus a remote group during the Autumn 2025 and Spring 2026 terms. Eight to twelve weeks are allowed for recruitment, and randomisation will occur within a month of the groups beginning. We have deliberately avoided running MAC groups during the summer terms since our experience indicates poor uptake while young people are preoccupied by examinations (see **Figure 10**).

Participants' levels of depression will be measured using the SMFQ for young people and PHQ-8 for parent/carers fortnightly for 12 months following randomisation. All participants will also complete a full set

of measures at baseline, just after the MAC finishes (14 weeks post-randomisation) and 12 months post randomisation. Further details of how this work fits with the rest of the programme from the timeline are included in the Gantt chart (**Figure 11**)

Figure 10: RCT Milestones

2027: ECONOMIC MODELLING, MECHANISMS, ANALYSIS, DISSEMINATION

Figure 11: Whole Programme Gantt

20. CRITERIA FOR EARLY TERMINATION OF THE TRIAL

The trial has the following stop-review-go criteria based on recruitment, uptake of intervention, and drop out, that may lead to premature discontinuation of the trial.

STOP / REVIEW / GO criteria:

- 1. Mean recruitment of 40 adolescents per geographical site (target 48, stop if < 36),
- 2. Mean of 9 adolescents commence MAC from each site for each cohort of groups (target 12, stop if < 6),
- 3. Mean of 36 adolescents complete SMFQ at 3 months per site (target 40, stop if < 28).

Values in the review zones (36-39 recruited, 6 to 8 commenced, 28-39 retained) would require exploration for the potential to improve and continue with advice from the funders and the Trial Steering Committee.

21. DATA MANAGEMENT

Methods used to maximise completeness of data

We have worked with our PPIE collaborators and will continue to do so as well as with the newly formed Research Advisory Groups (RAGs) to support the development of standardised operating procedures on how we approach young people and families to ensure that the outcomes we are collecting are easy to complete and most relevant for the trial. We have built in regular checks on data completeness, including employing a researcher who will work across all sites to remind participants when follow-ups are due and gently reminding participants of overdue follow-ups. The participant incentive for taking part is offered in staggered payments that fall after each period of data collection (see **Table 3**).

Methods for ensuring secure storage of data

- All data will be collected and held in accordance with GDPR.
- Each young person, carer, and therapist will be assigned a unique identifier, which will be stored separately to all research data.
- Data collection will be managed by the CAM:IDE Team (University of Cambridge) and stored on servers located at the University West Site Data Centre.
- Identifiable data will be held in a REDCap server database, hosted on the ISO 27001 certified, NHS Toolkit compliant SafeHaven.
- Access to data will be restricted to the ATTEND research team.
- Levels of access will be set by assigning team members to defined User Roles within REDCap, to control both the blinding and restrict access to identifiable data.
- Deidentified data sets will be provided to Study Statisticians by the CAM:IDE Data Managers as required.
- Participants will be given the Privacy Notice (**Appendix n**) when consenting to take part.

Data collection methods

Scheduling of participant follow ups and the data collection will be carried out by Team Members allowed access to identifiable data (see **Table 7**), directly from the REDCap Database on the SafeHaven.

Both the fortnightly collection of the SMFQ or PHQ-8 for carers, and the Baseline and Follow-up measures will be achieved using the MyCap phone app, the data being returned directly to REDCap on the SafeHaven. Once initiated, scheduling and text message reminders are completely automated. Web links or paper forms can be provided for participants who prefer this, or without access to a phone. In the case of paper copies

being used, this data will be entered onto REDCap by one of the research team and then double checked by a different member of the research team. The paper copy of completed measures will then be securely scanned and uploaded to the participant's REDCap record. The original paper copy will be confidentially shredded. An additional variable will be added to the trial database to indicate if paper copies have been used so that it is easy to identify this form of data entry. The Apps will use secure end-to-end encryption and data security and handling will be General Data Protection Regulation (GDPR) compliant and will only be available for use by project participants.

We need to collect certain identifiable data in order to contact participants to arrange assessment and pass on important information. We are collecting the following participant identifiable data:

- Name
- Address
- Email
- Phone number
- GP name and address
- CAMHS/mental health service caseworker name and contact details.

This identifiable data will be obtained either via the Permission to Contact Form (**Appendix e**), in which case a member of the research team will enter it into the REDCap trial database or entered directly by the participant into REDCap.

Should this data be provided in paper format, it will be securely scanned and uploaded to REDCap with the original paper copy being confidentially shredded. Any identifiable data will be stored securely and separately from research data.

How long data will be stored for

The identifiable data listed above will be stored for the duration of the study on the SafeHaven platform. This is a prevention trial and so we hope to undertake a longer term follow up to see how benefits accrue during the next ~10 years (or when our youngest participant is 25) by linking to administrative datasets via their identifiable data, to compare key outcomes (attendance at school, A level results, post school education/training, admissions to A&E and further mental health treatment) to see if they differ between the intervention and control arms. Therefore, we offer participants the option to consent to the retention of their name, address, and date of birth following the study's completion, until we establish linkage with the National Pupil Database and various NHS England datasets, including HMRC, DWP, Hospital Episode Statistics, and the Mental Health Dataset. Our intention is to conduct this linkage post-trial, and five and ten years later, pending funding and the necessary ethical approvals which we will submit as an amendment. After this linkage, the identifiable information will be promptly deleted. Participants retain the right to opt out via the consent form. [name] and [name] hold overall responsibility for data storage and disposal of data from this project.

Data access

The de-identified research data will be as accessible as possible to other researchers who wish to use it, with requests being granted by the ATTEND Core Team as a group, using the standard ATTEND Publication Proforma. This also avoids duplication. Details in the ATTEND Dissemination Policy.

22. COMPLIANCE AND WITHDRAWAL

Intervention compliance

Whilst our primary analysis will be Intention-To-Treat, we will also run secondary complier average causal effect (CACE) analyses of the SMFQ primary outcome in young people. We will use the following criteria to determine if an 'adequate dose' of MAC has been received by the young person:

• Attend at least 4 MAC sessions(Dubicka & Bullock, 2017)

End of Trial definition

The end of the trial will be considered as the date on which the last participant has completed their follow-up assessment or qualitative component. The sponsor will notify the main Research Ethics Committee of the end of the trial within 90 days of its completion or within 15 days if the trial is terminated early.

Archiving

There is no requirement for physical archiving since all data will be stored electronically. Any information collected on paper will be securely scanned and confidentially shredded. All electronic data will remain encrypted, and password protected and saved in a study specific SharePoint hosted by the University of Cambridge.

Trial Governance

[name] and [name], as joint Chief Investigators will assume responsibility for the financial management and delivery of the trial, supported by [name] as Programme Manager and [name] as Trial Manager. [name] will lead the Core Trial Team of PPIE Collaborators, Site Leads, RCT Researchers, Trial Statistician, Junior Statistician, Trial Health Economist and Junior Health Economist who will meet monthly via teleconference. These meetings will be used to monitor progress against the proposed timeline, to discuss recruitment and coordinate findings between the different work-streams as they arise and to discuss and solve possible risks or barriers to the delivery of the project. Weekly researcher meetings will be led by [name] as the Trial Manager to keep track of the day-to-day running of the RCT.

Our independent Steering Committee is chaired by [name], Associate Professor, of the Care Policy and Evaluation Centre, London School of Economics and the Committee's role will be to provide critical scrutiny to the conduct of the programme overall and they will meet at least annually with the option of convening more frequently if required. Data Monitoring and Ethics Committee (DMEC) meetings will take place shortly prior to each TSC meeting. The Trial Statistician will request data extracts prior to the DMEC meeting and prepare open and closed DMEC reports (see **Table 7** for information regarding blinding) summarising data quality and safety information. The Chair of the DMEC will be provided to the TSC after each meeting.

Risk Management

This trial will inevitably involve participants who are vulnerable by virtue of their age and mental health. The latter may also apply to parent/carers. It is therefore essential that we have strong standardised operational procedures to ensure participant safety should risk of harm to self or others become evident, or if safe-guarding concerns emerge. Clinical responsibility for all young people will remain with their referring clinician. We will ensure that one person with Level 3 child protection training is available during office hours at all times to support Junior Researchers who are concerned about participants, as well as liaising closely with the referring clinician teams and ensuring that junior staff have basic child protection and risk management training.

Should young people or carers disclose a risk of harm to self or others a separate Risk Protocol will be actioned (**Appendix o**). This Risk Protocol will involve the completion of a standardised pro forma which will be signed by the local site lead and sent to the Trial Manager within 24 hours. The Trial Manager will complete a Serious Adverse Event form (SAE) (**Appendix o**) sending a copy to the Trial Steering Committee and to the East of England – Cambridge South Research Ethics Committee (24/EE/0091). The Participant Information Sheet (**Appendix d**) informs young people and carers that if they disclose information of potential harm to themselves or someone else, we will need to break confidentiality. Although young people will be referred to the study from clinical services in health or school settings and may remain linked to these services during the study, some young people may be discharged during the

follow-up period, and we will therefore need additional procedures in place to ensure the safety of this group. Service organisation varies between our sites, so we will prepare site specific standardised operating procedures in partnership with the involved teams. Where local services are unable to maintain clinical responsibility for young people, this role will be fulfilled by the young person's General Practitioner (GP). We will also record details of the parent/carer's GP in case we need to notify them of any risk to their patient.

[name] and [name], with the support of [name] and [name], will be responsible for identifying and managing risks and potential barriers. They will undertake a formal risk assessment and maintain a risk register. Risk or barriers to delivery will be a standing item for all team meetings to ensure the early identification of any issues arising, and to enable us to take timely remedial or mitigating action. If difficulties were not rapidly resolvable, we would inform the Trial Steering Committee and our grant manager at NIHR as appropriate.

Research ethics approval

We have received multi-centre ethical approval from the East of England – Cambridge South Research Ethics Committee (ref number 24/EE/0091) and local research governance approval for all sites (Devon Partnership Trust, South London and Maudsley Trust, Sussex Partnership NHS Foundation Trust, Nottinghamshire Healthcare NHS Foundation Trust, and Oxford Health NHS Foundation Trust). The study personnel, management group and independent Trial Steering Committee, chaired by [name] will ensure that the study is conducted within appropriate NHS and professional ethical guidelines, ensuring that Good Clinical Practice guidelines are observed at all times. The core research team will all complete Good Clinical Practice Training and we will ensure that any Junior Researchers supporting the trial are also trained.

We intend to publish this protocol via a publicly available Open Science Framework. For any amendment to the trial, the Chief Investigator or designee, in agreement with the sponsor will submit information to the appropriate body for them to issue approval for the amendment. Any amendments will be handled in line with the HRA IRAS amendments protocol, and our sponsor will submit a valid notice of amendment to the REC for consideration and follow the HRA IRAS processes.

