In-person groups will be held in central locations to maximise attendance, with both young people and parent/carer groups at the same location. Where possible these two groups will run simultaneously to aid travel for the young person and their parent/carer, however, where this is not possible, they will occur in the same week. In person groups will only involve participants from the same site joining together.

Remote groups will be conducted using NHS approved software, for example MS Teams or Zoom. Participants will be encouraged to have their video cameras on during the MAC sessions since we know this improves engagement and this will be emphasised during the orientation meeting. Remote groups will involve participants from multiple sites and will run once enough participants have selected this as an option. All materials that would usually be given in person to participants will be posted to participants' homes or emailed, depending on preference. Remote and in person MAC groups will cover exactly the same content in exactly the same order, their only difference being their mode of delivery.

WHEN and HOW MUCH

The interventions will consist of 8 weekly group-based sessions of 1 hour 30 to 45 minutes duration and a pre-class interview of 1 hour duration conducted with each dyad of a young person and their parent/carer and allowing for individual therapist contact with both. Participants of both groups will be asked to engage

in regular daily home practice consisting of guided meditation and generalisation exercises aimed at helping participants utilise mindfulness skills in daily life.

HOW WELL

- Therapist completed supervision forms indicate issues that therapists wanted guidance about.
- Session checklists will be used to record if all elements of a session were delivered as intended.
- Data from the practice Apps will indicate the number and duration of practice sessions conducted by YP and parents/carers.

Supervision

Therapists will take part in 9 supervision sessions: Week 0 before orientation and session 1 begins, through to week 9 after the final session has been delivered. Therapists will access remote group supervision with experienced MAC therapists. The 60-minute supervision would comprise 45 minutes on the young person intervention and 15 minutes on carer intervention, with a strong focus on overlap. A brief pre-supervision form will be developed, which therapists will complete to highlight demands to discuss at supervision.

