14. OUTCOMES

Outcome measures (**Appendices j and k**) were chosen in close collaboration with young people and parents to reflect target psychopathology, key therapeutic components, and clinical processes. Participants will need to have completed all intake and baseline measures before they are randomised.

- Young people will then complete the Short Mood and Feelings Questionnaire SMFQ; (Angold et al., 1995) every fortnight for 12 months.
- Parents/carers will then complete the Generalised Anxiety Disorder GAD-7; (Spitzer et al., n.d.-a) every fortnight for 12 months.

The full complement of measures as listed in **Table 5** will be completed by both groups 14 weeks and 12 months after randomisation. If participants withdraw from treatment, we will continue to request outcome measures from them for the 12-month follow-up, unless they choose to formally withdraw from the trial completely.

Timepoint Data Collected Young People Parent/Carer T1: T2: Construct **TO:** Completed Completed 3.5m 12m B/L F/U F/U Eligibility CRIES-8 (Perrin et al., **PTSD** screen At intake assessment 2005) 33 item MFQ (COSTELLO & ANGOLD, Current low mood At intake assessment 1988; Daviss et al., 2006) **Baseline Outcomes Current depression and** RCADS 25 (Ebesutani et Х anxiety severity al., 2012) Past trauma and YCAS (Schlechter et al., YCAS (Schlechter et al., Х adversity 2021) 2021) Own and child's Race/ethnicity, family, current living situation^c Child's DOB, gender, current medication for Respondent anxiety or depression, Х Background past treatment for depression and anxiety^c Own occupation, personal history of depression, education background Site option Face-to-face or remote Х

Table 5: Outcome Measures

Primary outcome					
YP Depression	SMFQ (Angold et al., 1995)		Repeate intervals follow-u	d at 2 wee throughc p	ekly out
Secondary outcomes					
P/C Depression		PHQ (Kroenke et al., 2009b)	Repeated at 2 weekly intervals throughout follow-up		
YP Depression	33 item MFQ (COSTELLO & ANGOLD, 1988; Daviss et al., 2006)		х	x	x
Anxiety	RCADS 25 (Ebesutani et al., 2012)	GAD-7 (Spitzer et al., n.db)	х	х	х
Quality of Life ^a	EQ-5D-5L (Devlin et al., 2018b)	EQ-5D-5L (Devlin et al., 2018b)	et al., X X		х
Coping	1 bespoke question	1 bespoke question	Х	Х	Х
Parent – young people relationship quality ^b	PARS (Burke et al., 2021)	PARS (Burke et al., 2021)	х	х	х
Health Economics Measures					
Services and personal costs		Child's resource use bespoke questionnaire ^c	х	х	х

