Participants will be asked to record their daily mindfulness practice, either directly via the app or on paper diary cards. We will measure number of times both formal and informal mindfulness has been practiced as well as recording which practices were used. Whilst self-report will be the primary source of this data, we will

cross reference this with metrics recorded directly via the app, for example, the dates, duration, and frequency of log-ons as well as how often each audio recorded mindfulness practice was played.

Health Economic Measures

Cost components included in the health economic analysis will comprise:

- Detailed costs of the MAC intervention,
- Other NHS and social service use during the 12-month within-study period, including:
 - CAMHS, primary care, social care, and community care contacts,
 - \circ prescribed medications,
 - hospital inpatient admissions and outpatient attendances,
 - School attendance and other education-related contacts
- Informal care costs incurred by participants, parents and carers and families, including time taken off work.

The intervention costs will comprise the costs of:

- training the trainers,
- staff time to deliver MAC classes and pre-class orientation interviews,
- non-staff costs associated with delivery of MAC classes (e.g., life or virtual room hire),
- the costs of delivering the app, and
- provision of information materials for participants and families.

The volume of resource use for the non-intervention cost components will be measured in the trial using a bespoke retrospective questionnaire based on a modified version of the Client Service Receipt Inventory, completed by participants for a 12-month period at baseline, 14 weeks, and 12-months post-baseline for each individual participant. These questionnaires will cover the previous 3-month period at baseline and 3 months, and the previous 9-month period at 12 months.

When parents/carers have consented to take part we will ask them to complete this information on behalf of their child. If the young person's parent/carer has not consented for their own involvement, then we will ask the young person themselves to complete this questionnaire.

EQ-5D-5L Quality of Life (Devlin et al., 2018a)

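### The only stated route to an SAE form is a disclosed risk of harm, which leaves by-arm SAE counts open to unequal ascertainment, probably towards more SAEs in MAC

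*Protocol*

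**What the plan says.** Section 22, Risk Management, sets out a chain. It starts with "Should young people or carers disclose a risk of harm to self or others a separate Risk Protocol will be actioned". A standardised pro forma is signed by the site lead and reaches the Trial Manager within 24 hours. Then: "The Trial Manager will complete a Serious Adverse Event form (SAE". The same subsection opens with a wider aim, procedures to protect participants "should risk of harm to self or others become evident, or if safe-guarding concerns emerge", but does not tie that wider wording to the SAE form.

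The only other mention of serious adverse events is in Table 6 (section 15), on whether a blinded team member may need to know an allocation. The text shown has no SAE definition and no scheduled adverse-event enquiry.

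On contact, section 13 gives the MAC arm "8 weekly group-based sessions of 1 hour 30 to 45 minutes duration and a pre-class interview of 1 hour duration", and carers have parallel groups. For both arms, section 14 says the full set of measures "will be completed by both groups 14 weeks and 12 months after randomisation". Section 21 has the fortnightly questionnaires collected through an app: "Once initiated, scheduling and text message reminders are completely automated".

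Inpatient admissions are collected in both arms as a cost item (section 14, Health Economic Measures: "hospital inpatient admissions and outpatient attendances"), and mortality for QALYs (section 18). Neither is linked to SAE reporting. Safety information is summarised in open and closed DMEC reports (section 22, Trial Governance), which Table 7 expects the DMEC to see split by group.

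**The concern.** Two things go wrong if the written chain is followed. First, it counts the wrong object. A disclosed risk is not an event, yet it generates an SAE form. A hospital admission or a death is an event, yet it has no stated path to a form unless someone has also disclosed a risk.

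Second, the count depends on the opportunity to disclose to the trial, and the design gives one arm more of it. If MAC showed more SAEs than TAU, the DMEC could not tell extra contact from real harm. A true excess could be explained away, and an artefact could raise a false alarm. Analysis cannot repair this later, because an event never recorded as an SAE is absent from the SAE data. What triggers a form is a rule of trial conduct that this document fixes, so it is not a detail that can wait for the SAP.

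**Working it through.** **Extra contacts.** Section 13 gives 8 sessions and 1 interview, so 8 + 1 = 9 contacts per MAC young person. In hours: 1 + 8 × 1.5 = 13 to 1 + 8 × 1.75 = 15. The carer's parallel group comes on top.

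**Shared contacts after randomisation.** There are 2 full assessments (14 weeks and 12 months) and about 52/2 = 26 fortnightly prompts. The documents do not say whether an automated prompt is a real opportunity to disclose, so both counts are tried: k = 2 without prompts and k = 2 + 26 = 28 with them.

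**Illustration of detection (assumed model).** Suppose the true event rate is equal in both arms and each opportunity brings a disclosure with the same probability p. The documents give no p; 0.01 to 0.20 is assumed.

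- P(recorded, TAU) = 1 − (1 − p)^k
- P(recorded, MAC) = 1 − (1 − p)^(k + 9)

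| Shared opportunities k | p | TAU | MAC | Ratio MAC:TAU |
|---|---|---|---|---|
| 2 | 0.01 | 0.020 | 0.105 | 5.26 |
| 2 | 0.05 | 0.098 | 0.431 | 4.42 |
| 2 | 0.20 | 0.360 | 0.914 | 2.54 |
| 28 | 0.01 | 0.245 | 0.311 | 1.27 |
| 28 | 0.05 | 0.762 | 0.850 | 1.12 |
| 28 | 0.20 | 0.998 | 1.000 | 1.00 |

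**As counts.** With 240 per arm and an assumed true event risk of 10%, each arm has 240 × 0.10 = 24 events. At p = 0.05 the trial would record about 2.3 in TAU and 10.3 in MAC if only the two assessments count, or 18.3 and 20.4 if the prompts count too.

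The ratio thus lies between 1.00 and 5.3, depending on two things the documents do not state. An enquiry on the same schedule in both arms would give a ratio of 1.00 from that source, provided participants respond equally.

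**Does any other route reach an SAE form?** Admissions and mortality are collected in both arms but stop at the economic analysis. The monthly Treatment Recording Sheet (TRS, section 14) covers both arms but records therapy content. Liaison with referring teams is promised in section 22, but not as a reporting rule. In the text shown, none of these reaches an SAE form.

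**The case against.** The strongest reply is that the Risk Protocol and SAE form are in Appendix O, and that section 22 also promises site-specific procedures, extra procedures for discharged young people and Good Clinical Practice. None of these is shown, and any could define SAEs more widely. This stands. The point is about the main text, and a reader who inferred that undisclosed admissions or deaths generate no SAE at all would go beyond the evidence.

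Trial contact in TAU is also not nil. Section 21 employs a researcher to remind participants, Table 7 lists outcome assessors, and the TRS gives a monthly clinician channel in both arms. Further, section 13 reports that in the development work TAU participants received more treatment while clinicians often had less frequent contact with those allocated to MAC, and it expects something similar here. If clinicians relay events to the trial, that channel could favour detection in TAU, a possibility the illustration above leaves out. So the net direction is probable, not certain.

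Two stronger readings are tempting. One is that the between-arm harms comparison is biased. The protocol specifies no formal harms comparison, and the size of any distortion is unknown, including none. The other is that the trial could conclude nothing about safety. Admissions, deaths and fortnightly symptom scores are collected in both arms, so that does not follow. Nor does the carer PHQ-8's omission of the suicide and self-harm question bear on the difference, since carers in both arms complete the same form.

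**Conclusion.** The point holds in limited form. In the protocol text shown, one SAE route is stated. It turns on disclosure rather than on an event, and MAC participants have 9 more trial-therapist contacts in which to use it. By-group SAE counts for the DMEC, and any later harms reporting, are open to unequal ascertainment, probably inflating MAC.

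The 9 contacts follow directly from section 13. The range of 1.00 to 5.3 rests on assumed disclosure probabilities, equal true event rates and no differential clinician reporting; it illustrates the problem and is not an estimate. The conclusion would weaken if Appendix O defines SAEs by event and provides the same enquiry in both arms. The main text should be changed because the remedy is cheap and missed events may not be recoverable as SAEs.

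**What to change.** In section 22, Risk Management:

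1. Keep a disclosure as a risk event that triggers the Risk Protocol exactly as now, and log its source (MAC session, researcher contact, questionnaire, clinician).
2. Define an SAE by event. In addition to immediate reporting, ascertain SAEs on the same schedule in both arms at T1 and T2 by linking the admissions in the resource-use questionnaire and the mortality data to SAE reporting. A tick-box on the monthly TRS is an optional addition.
3. Report event-based SAEs, and risk events by source, to the DMEC separately by arm.

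Align Appendix O with this wording, or cite it in the main text if it already says so.

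The cost is revised wording in the protocol and Risk Protocol, one REDCap source field, the data link and, if wanted, the TRS tick-box. The added sources have limits. Questionnaire-reported admissions arrive late, rest on up to 9 months' recall and cover the young person only, so carer events would be missed. TRS completion depends on clinician contact, which may differ by arm. They supplement immediate reporting and do not replace it.
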